2.0 OBJECTIVES**2.1 IMMUNOGENICITY**

The immunogenicity objective of this study is to evaluate the effects of a single 40- μ g dose of rBV A/B on the botulinum toxin type A and type B neutralizing antibody concentration (NAC) over a 12-week period following vaccination in participants previously immunized with PBT (or PBT and rBV A/B) for occupational protection.

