3.3 ENDPOINTS

3.3.1 Immunogenicity

The primary immunogenicity endpoint is the proportion of participants achieving a four times or greater increase in NAC by Week 4 compared with Week 0. A positive response will be defined as achieving this level of increase in at least 50% of the participants for botulinum toxin type A and type B.

The secondary immunogenicity endpoints are as follows:

- The proportion of participants achieving a two times increase in the area under the plasma concentration-time curve between Week 0 and Week 12 in NAC in comparison to a straight-line extension of the Week 0 NAC to Week 12. A

positive response will be defined as achieving this level of increase in at least 50% of the participants for botulinum toxin type A and type B.

- The proportion of participants achieving a three times or greater increase in NAC by Week 4 compared with Week 0. A positive response will be defined as achieving this level of increase in at least 50% of the participants for botulinum toxin type A and type B.

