8.2.4 Immunogenicity Analysis

The immunogenicity population will be used for all immunogenicity endpoints. The per protocol population will be used in the case that any sensitivity analyses are deemed necessary.

The immunogenicity parameters are concentrations of neutralizing antibodies against botulinum toxin type A and toxin type B. These parameters will be analyzed by using NAC data from a validated mouse neutralization assay.

For the primary endpoint, a positive response will be defined as achieving a greater than or equal to four times increase (point estimate) above baseline in NAC by Week 4 compared with Week 0 in at least 50% of the participants in the immunogenicity population for botulinum toxin type A and type B, respectively.

A point estimate and two-sided 95% confidence interval for the proportion of participants who achieve this endpoint will be provided.

For the first secondary immunogenicity endpoint, a positive response will be defined as achieving a two times increase above baseline in the estimated area under the plasma NAC-time curve in the period from Week 0 to Week 12 in comparison to straight-line extension of the Week 0 antibody concentration from Week 0 to Week 12 in least 50% of the participants.

For the second secondary immunogenicity endpoint, a positive response will be defined as is achieving a three times or greater increase in NAC above baseline by Week 4 in at least 50% of the participants for botulinum toxin type A and type B. A point estimate and two-sided 95% confidence interval for the proportion of participants who achieve this endpoint will be provided.

Further details of the analysis, will be provided as needed in a separate statistical analysis plan.

In the event that the primary endpoint is not met for neutralizing antibodies against botulinum toxin type A and type B, the sponsor-investigator will determine if the plasma collected during the study contains sufficient antibody titers for meeting specifications for BabyBIG production. If the immune responses meet specifications to permit the production of BabyBIG, then the trial will still be considered successful. Also, a second booster dose of rBV A/B vaccine may be considered; however, this will require operational modifications (e.g., a protocol amendment and updated consent form).

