1.2 STUDY OBJECTIVES

1.2.1 Immunogenicity

The immunogenicity objective of this study is to evaluate the effects of a single 40- μ g dose of rBV A/B on botulinum toxin type A and type B neutralizing antibody concentrations (NAC) over a 12-week period following vaccination in participants previously immunized with PBT (or PBT and rBV A/B) for occupational protection.

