7.1 ANALYSIS OF PRIMARY IMMUNOGENICITY ENDPOINT

The primary immunogenicity endpoint is the proportion of participants achieving a four times or greater increase in NAC by Week 4 compared to Week 0. The cut-off value for determining whether the increase is achieved for each subject will be calculated as $[(\text{Week 0 value}) \times 4] + (\text{Week 0 value})$. A positive response will be defined as achieving this level of increase in NAC in at least 50% of participants. The proportion of participants who achieve this level of increase in NAC will be provided along with a 95% confidence interval. Graphs may be used to show corresponding participant-level data.

This primary analysis will be performed for both botulinum toxin type A and type B. In the event that the primary endpoint is not met for neutralizing antibodies against botulinum toxin type A or type B, the Sponsor-Investigator will determine if the plasma collected during the study contains sufficient antibody titers for meeting specifications for BabyBIG production. If so, the trial will still be considered successful.

Details regarding the collection schedule for blood samples for NAC can be found in Section 7.3.

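### After a missed primary endpoint the trial can still be called successful on plasma usability, which does not answer the immunogenicity objective, and the two documents word the trigger differently

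*SAP*

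**What the plan says.** Protocol 3.3.1 defines a positive response as "achieving this level of increase in at least 50% of the participants for botulinum toxin type A and type B", the increase being at least four times the Week 0 NAC by Week 4. Protocol 8.2.4 repeats this and applies it "in at least 50% of the participants in the immunogenicity population for botulinum toxin type A and type B, respectively".

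Both analysis sections then add a fallback.

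- **Trigger, Protocol 8.2.4:** "In the event that the primary endpoint is not met for neutralizing antibodies against botulinum toxin type A and type B".
- **Trigger, SAP 7.1:** the endpoint is "not met for neutralizing antibodies against botulinum toxin type A or type B, the Sponsor-Investigator will determine if the plasma" is adequate for BabyBIG production.
- **Consequence, Protocol 8.2.4:** "If the immune responses meet specifications to permit the production of BabyBIG, then the trial will still be considered successful".
- **Consequence, SAP 7.1:** "If so, the trial will still be considered successful".

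The endpoint definitions themselves (Protocol Synopsis, Protocol 3.3.1, SAP 3.2.1) contain no such rule. The immunogenicity objective is the effect of the dose "on the botulinum toxin type A and type B neutralizing antibody concentration (NAC) over a 12-week period" (Protocol 2.1); SAP 1.2.1 states the same aim.

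**The concern.** The fallback answers a different question from the one it replaces. The primary endpoint asks whether the dose raised each participant's antibody level relative to Week 0. The fallback asks whether the plasma in hand reaches a production level. Everyone enrolled has been immunized before, and Protocol 1.1 says that such people with circulating A and B antibody can already donate for BabyBIG. Antibody present before the study dose could therefore help the plasma pass. The documents do not show that unboosted plasma would pass, but they do not exclude it, and there is no control arm.

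At stake is the trial-level conclusion. After a miss, a reader told that the trial succeeded could take this to mean that the vaccine had the intended effect on NAC. Separately, if the two triggers are read literally, a miss on one toxin opens the fallback under the SAP and has no rule under the protocol.

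**Working it through.** **1. The two criteria side by side**

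| | Primary criterion | Fallback |
|---|---|---|
| Quantity | Rise in NAC by Week 4 | Titer of collected plasma |
| Reference | Participant's own Week 0 value | Production specification; no Week 0 comparison stated |
| Threshold | Four times or greater, in at least 50% | No value or source given in either document |
| Who contributes | Immunogenicity population | Participants who chose to donate and were eligible (Protocol Synopsis, 5.2.2.2) |
| Planned output | Proportion with 95% CI | None against a specification; SAP 9.0 only summarizes and lists plasmapheresis data |
| Decided by | Observed proportion | Sponsor-investigator's determination |

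**2. How much the fallback could matter**

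The plan states no power, alpha or expected response rate, so there is no figure to reproduce. The probability of passing the fallback, f, cannot be derived. Its role can be shown at assumed rates.

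Let q(p) = P(X ≥ 25) for X ~ Binomial(50, p), taking the stated maximum of 50 participants. At a true responder rate of 40% for each toxin, q = 0.09781. With independent toxins, both meet the criterion with probability 0.09781² = 0.0096. Under the SAP trigger:

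P(called successful) = 0.0096 + 0.9904 × f

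This is 0.010 at f = 0, 0.505 at f = 0.5, 0.901 at f = 0.9 and 1 at f = 1. In that setting the label depends almost wholly on f, about which the documents say nothing.

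**3. The trigger wording**

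On the literal reading, the documents part company when exactly one toxin misses. For independent toxins:

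P(exactly one misses) = qA(1 − qB) + qB(1 − qA)

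For n = 50: q(0.30) = 0.00237, q(0.40) = 0.09781, q(0.50) = 0.55614, q(0.60) = 0.94266, q(0.70) = 0.99907.

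Worked case, A 60% and B 40%: 0.94266 × 0.90219 + 0.09781 × 0.05734 = 0.8505 + 0.0056 = 0.856.

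| Assumed true rates A/B | P(exactly one misses), n = 50 |
|---|---|
| 30/30 | 0.005 |
| 40/30 | 0.10 |
| 40/40 | 0.18 |
| 50/50 | 0.49 |
| 60/60 | 0.11 |
| 70/60 | 0.06 |
| 70/70 | 0.002 |
| 60/40 | 0.86 |
| 70/30 | 0.997 |

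With n = 30 (at least 15 responders), q(0.40) = 0.17537, q(0.60) = 0.90294 and q(0.70) = 0.99363. The chance is then 0.01 at 70/70, 0.10 at 70/60 and 0.76 at 60/40.

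If the toxins are fully correlated, the chance is |qA − qB|. For n = 50 this is 0 at equal rates, 0.06 at 70/60 and 0.84 at 60/40.

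**The case against.** The rule is prespecified and openly stated in both documents. The miss is named as a miss, and the proportion with its interval is reported whatever happens. Both secondary endpoints are also comparisons with Week 0 and would be reported. Producing BabyBIG is the declared ultimate goal (Protocol 1.2) and collecting plasma is a study objective, so calling a trial with usable plasma successful has a stated basis. BabyBIG is an approved product, so its specifications may well exist elsewhere. The protocol also mentions a possible second booster, subject to an amendment, so it foresees further action after a miss. Finally, because the protocol criterion is set for each toxin, failing it can naturally mean failing either, which is what the SAP says.

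All of this is fair, and it limits the point: no estimate or interval is altered, and no alpha is inflated. It does not remove the trial-level label, which gives a missed primary endpoint the same headline as a met one on evidence of a different kind. Usability for production already has a place, the exploratory objective and endpoint. The booster sentence describes an optional later step and leaves the success rule as it is. The collective reading of the protocol trigger is available but not explicit, so one clear wording is still needed.

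**Conclusion.** The concern holds, as a change that should be made. After a missed primary endpoint, the plan as written permits a success conclusion that does not address the immunogenicity objective. This follows from the text alone and rests on no numerical assumption. Its probability cannot be given, because the specification value, the baseline NAC and the expected number of donors are all absent from the documents.

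The difference between the triggers is the smaller issue. It matters only on the literal reading. It is negligible when both response rates lie well to the same side of 50%, and substantial when they are near 50% or straddle it. Those figures depend on assumed rates, an assumed n and assumed dependence between toxins.

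**What to change.** Use the same text in Protocol 8.2.4 and SAP 7.1, replacing the sentence on success:

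> If the 50% criterion is missed for type A or for type B, the primary endpoint is reported as not met for that toxin. Whether collected plasma meets the BabyBIG production specifications [cite document and version] is reported separately, with the exploratory endpoint in the plasma-donating population and next to donors' Week 0 NAC. It does not change the primary conclusion.

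Add the matching display to SAP 9.0.

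No new data are required: Week 0 NAC and NAC with each donated unit are already collected (Protocol 5.1, SAP 1.6). The cost is a SAP revision and a protocol amendment under Protocol 9.4, which involves IRB approval and a regulatory submission. The sponsor gives up a more favourable headline if the endpoint is missed. Use of the plasma is unaffected.

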7.2 ANALYSIS OF SECONDARY IMMUNOGENICITY ENDPOINTS

All secondary immunogenicity endpoints will use the immunogenicity population.

The first secondary immunogenicity endpoint is the proportion of participants achieving a two times increase in the estimated area under the plasma concentration-time curve in the period between Week 0 to Week 12 in comparison to straight-line extension of the Week 0 NAC to Week 12. The cut-off value for determining whether

the increase is achieved for each subject will be calculated as (Week 0 value) x (total number of days from Week 0 to Week 12 collection) x 2. A positive response will be defined as achieving this level of increase in at least 50% of the participants. If a participant does not have NAC collections through Week 12, the date of the last NAC collection will be used in place of the Week 12 date for both the concentration-time curve and the straight-line extension. In the cases where there are multiple NAC values on the same date for a particular subject, the mean of those values will be used in calculating the estimated area under the plasma concentration-time curve.

The second secondary immunogenicity endpoint is the proportion of participants achieving a three times or greater increase in NAC above baseline by Week 4 compared to Week 0. The cut-off value for determining whether the increase is achieved for each subject will be calculated as [(Week 0 value) x 3] + (Week 0 value). A positive response will be defined as achieving this level of increase in at least 50% of the participants.

Proportions will be provided for both secondary endpoints along with 95% confidence intervals.

Further details regarding the collection schedule for blood samples for NAC can be found in Section 7.3.

7.3 NEUTRALIZING ANTIBODY CONCENTRATION (NAC) VALUES

NAC determinations will be performed at Battelle Biomedical Research Center (Columbus, Ohio) by using a fully validated mouse neutralization assay used for all NAC determinations in the BabyBIG program.

Blood collection for determination of NAC values will be performed prior to vaccination at the Vaccination Visit (Day 0), for non-plasma donating participants at the Week 4 visit, and for plasma-donating participants at plasmapheresis visits and the Week 12 final study.

For summary tables involving NAC values, the week numbers will be assigned as described below. Week 4 and Week 12 have larger windows than other weeks in order to facilitate collection of NAC values during the time periods of primary interest.

Week 1 - values collected from Day 4 through Day 10

Week 2 - values collected from Day 11 through Day 17
Week 3 - values collected from Day 18 through Day 23
Week 4 - values collected from Day 24 through Day 32 [Day 28 (± 4 days)]
Week 5 - values collected from Day 33 through Day 38
Week 6 - values collected from Day 39 through Day 45
Week 7 - values collected from Day 46 through Day 52
Week 8 - values collected from Day 53 through Day 59
Week 9 - values collected from Day 60 through Day 66
Week 10 - values collected from Day 67 through Day 73
Week 11 - values collected from Day 74 through Day 79
Week 12 - values collected from Day 80 through Day 88 [Day 84 (± 4 days)]
Week 13 - values collected from Day 89 through Day 94
Week 14 - values collected from Day 95 through Day 101

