
STUDY SYNOPSIS (continued)

Name of sponsor company: California Department of Public Health (CDPH)
Name of investigational product: Recombinant Botulinum Vaccine A/B (rBV A/B)
Names of active ingredients: Recombinant Botulinum Antigen A and Antigen B adsorbed to 0.2% (wt/vol) Alhydrogel™
Test product, dose, and mode of administration: rBV A/B injections will consist of 40- μ g of total antigen (20 μ g of Antigen A and 20 μ g of Antigen B) adsorbed to 0.2% (wt/vol) Alhydrogel™, in a total dose volume of 0.5 mL. The vaccine will be administered by intramuscular injection in the deltoid muscle, preferably in the nondominant arm.
Reference therapy, dose, and mode of administration: No reference therapy will be employed.
Duration of treatment: Vaccine administration for all enrolled participants will occur at Day 0, and participants may elect to undergo plasmapheresis up to two times a week for up to 12 weeks, with the final on-site visit at Week 12 (\pm 4 days) and follow-up phone call for safety assessment at Week 26 after vaccination. Participants can elect to continue plasmapheresis up to 14 weeks post-vaccination as long as long as they continue to meet source plasma donor eligibility requirements..
Criteria for Evaluation
Populations: The immunogenicity population will include all participants who have received the study vaccine at the assigned dosage and for whom at least one post-baseline NAC was collected within 4 weeks of vaccination. For each post-vaccination assessment time point, the per protocol population will include all participants who received the vaccine dose, have a baseline NAC, and have all immunogenicity assessments completed within the protocol-specified timelines (including visit windows) for the time periods summarized and do not have major protocol violations expected to affect immunogenicity. A determination of major protocol violations expected to affect immunogenicity will be done by the sponsor-investigator before reviewing the immunogenicity data for the applicable participant.

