Diary review			X					
Serious adverse event collection ^r		X	X	X	X		X	X
Concomitant medication information	X ^t		X ^s	X ^s	X ^s		X ^s	X ^s
Phone call			X	X	X			X

HBV = hepatitis B virus; HCV = hepatitis C virus; HIV = human immunodeficiency virus; NAC = neutralizing antibody concentration; rBV A/B = recombinant botulinum vaccine A/B.

a. Week 1, Week 4, and Week 10 Follow-up Calls must occur with ± 3 days of the scheduled time.

b. Final Study Visit will be an on-site visit at Week 4 for participants who opt not to participate or who have been determined to be ineligible for donation for the entire study. All final assessments occurring at Week 12 will occur at Week 4 for these participants.

c. Extension of plasmapheresis for up to 14 weeks is optional

- d. Final on-site Study Visit must occur within \pm 7 days of the scheduled time.
- e. Final follow-up call for safety must occur within \pm 1 week of the scheduled time.
- f. Plasmapheresis-specific informed consent formed will be signed at the source plasma center.
- g. Physical examination will be performed as part of source plasma donor screening at the plasma collection center
- h. Female participants of childbearing potential must have a negative pregnancy test within 24 hours prior to vaccination.
- i. Participants will have vital signs taken twice at Visit 1: prior to injection, and 30 minutes (\pm 5 minutes) after receiving the injection.
- j. HIV, HBV, and HCV tests will be performed on each donated source plasma unit
- k. Results from screening tests must be available before Vaccination Visit
- l. Study participants will go to central lab or plasma center for this draw (not an on-site visit).
- m. Baseline NAC sample must be collected before rBV A/B injection and before plasmapheresis
- n. Participants not donating plasma must go to site for NAC collection within \pm 3 days of the scheduled time.
- o. May occur up to twice a week for up to 14 weeks (if hemoglobin and total protein remain within acceptable range) following vaccination with rBV A/B.
- p. At this visit, participants will be monitored for at least 30 minutes after injection for a possible reaction.
- q. In the diaries, participants record adverse events in order to determine SAE, oral temperature and injection site information.
- r. Only serious adverse events and new onset chronic illnesses are to be queried for and collected

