5.2.2.6 Week 12 Visit

For all participants participating in plasma donation, the final on-site study visit must occur within 1 week of Week 12. During this visit, the following activities will occur:

- Injection site inspection
- Review of serious adverse events or serious NOCIs

- Collection of concomitant medication information used for treatment of any SAEs or serious NOCIs, if any
- Collection of 20 mL of blood to determine NAC
- Urine pregnancy test for female participants of childbearing potential
- Completion of final on-site study record

Total blood volume collected at this visit will be 20 mL for NAC determinations. Total urine volume collected will be approximately 10 mL for the urine pregnancy test.

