1.6 STUDY PROCEDURES

The study will begin with a 7-day screening period (Days -7 to -1), during which participant eligibility will be determined. Screening must occur 1 to 7 days before the Vaccination Visit (Day 0).

Participants will enter either a 4-week treatment period (for non-plasma donors) or a 12-week treatment period (for plasma donors). At the Vaccination Visit (Day 0), the first day of the treatment period for all subjects, participant eligibility will be reviewed and blood collection will be performed to determine baseline NAC. After these assessments, a single rBV A/B injection will be administered to stimulate the production of antibodies against botulinum toxin type A and type B. Safety assessments will be performed before and after the injection, and a diary will be distributed to the participant to record injection site information, systemic reactions, and concomitant medications over the next seven days.

Study personnel will call all participants at Week 1 (\pm 3 days) to review the diary, injection site reactions, and any potential serious adverse events (SAEs) or new onset chronic illnesses (NOCIs) occurring over the past week.

Participants who receive the rBV A/B vaccination may elect to participate as source plasma donors if they meet the donor eligibility criteria of the sponsor-approved licensed source plasma collection site. Participants who elect to donate source plasma may begin following the Week 1 safety phone call and may donate up to twice per week through Week 12, with the possibility of continuing through Week 14 post-vaccination if they continue to meet source plasma donor eligibility criteria. The assessments to be completed at the visits to the plasma collection center are listed in the protocol and include a blood collection for NAC determination.

Safety assessments for non-plasma donors are scheduled on Week 0, Week 1 (\pm 3 days) (by phone), and Week 4 (\pm 3 days) (final on-site visit). Safety assessments for plasma donors are scheduled at Week 0 with follow-up phone calls at Weeks 1 (\pm 3 days), 4 (\pm 3 days) and 10 (\pm 3 days), and a final on-site study visit at Week 12 (\pm 7 days) to assess general health status and query for the interim occurrence of SAEs or NOCIs, if any.

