3.4 VISIT WINDOWS

Immunogenicity values (NAC values) will be assigned to weeks/visits according to the visit windows listed in Section 7.3. For displays using the per protocol population, immunogenicity assessment values which are collected outside the visit windows for the relevant time points will be excluded from per protocol analyses.

Safety values will be evaluated and displayed as belonging to the intended visit, regardless of the actual study day on which they were collected.

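### The Week 12 visit window is ±7 days in the protocol body but ±4 in the synopsis; SAP 7.3 uses Day 80 to 88, so some compliant final-visit samples are not counted as Week 12

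*SAP*

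**What the plan says.** **Visit window.** Protocol 5.2.2.6 says that for plasma donors "the final on-site study visit must occur within 1 week of Week 12". Note d to Table 1, in both the protocol and the SAP, gives ±7 days, as does SAP 1.6. The protocol synopsis differs: under duration of treatment it describes dosing and plasmapheresis, "with the final on-site visit at Week 12", and then gives a tolerance of ±4 days.

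**Sample.** The visit yields an immunogenicity sample: "Total blood volume collected at this visit will be 20 mL for NAC determinations" (Protocol 5.2.2.6).

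**Analysis window.** SAP 7.3 defines "Week 12 - values collected from Day 80 through Day 88", which it also expresses as Day 84 ±4. Week 11 is Day 74 to 79 and Week 13 is Day 89 to 94.

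**Consequence of the window.** SAP 3.4 assigns NAC values to weeks by the SAP 7.3 ranges and adds that "immunogenicity assessment values which are collected outside the visit windows for the relevant time points will be excluded from per protocol analyses". SAP 2.1.2 instead defines the per protocol population by the timelines and visit windows that the protocol specifies.

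**AUC.** The cut-off in SAP 7.2 is twice the Week 0 value times the number of days to the Week 12 collection. If collections do not reach Week 12, the last collection date replaces it on both sides of the comparison.

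**The concern.** An analysis window should contain the visit window it serves; otherwise a participant who keeps to the schedule is treated as off schedule. SAP 7.3 says that Week 4 and Week 12 were given wider ranges so that values at the periods of main interest would be captured. At Week 12 the range is narrower than the visit window in the protocol body.

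Three things are at stake:

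- **By-week NAC summaries.** A final-visit sample can appear under Week 11 or Week 13.
- **Per protocol Week 12 results.** SAP 2.1.2 and SAP 3.4 can give different answers for the same sample, so two programmers could build different sets.
- **End of the AUC.** The Week 12 collection is not defined for a final sample on Day 89 to 91.

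The study is open-label. If these choices stay open, they may be made after the NAC values are known.

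**Working it through.** **Inputs**

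- Visit window ±7 days: Protocol 5.2.2.6; note d to Table 1 in both documents; SAP 1.6.
- Visit window ±4 days: protocol synopsis.
- Week 11, 12 and 13 ranges (Day 74 to 79, 80 to 88, 89 to 94): SAP 7.3.
- Week 4 visit window ±3 days: Protocol 5.2.2.4. Week 4 range Day 24 to 32: SAP 7.3.
- AUC cut-off: SAP 7.2.

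**1. The SAP's own figure.** Week 12 is 12 × 7 = Day 84. Then 84 − 4 = 80 and 84 + 4 = 88. This reproduces SAP 7.3 and matches the synopsis.

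**2. Permitted days in the protocol body.** 84 − 7 = 77 and 84 + 7 = 91. The count is 91 − 77 + 1 = 15 days.

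**3. Labels under SAP 7.3**

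| Final-visit day | Label | Days |
|---|---|---|
| 77, 78, 79 | Week 11 | 3 |
| 80 to 88 | Week 12 | 9 |
| 89, 90, 91 | Week 13 | 3 |

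Outside Week 12: 3 + 3 = 6 days, and 6/15 = 40% of permitted days.

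**4. Week 4 for comparison.** 28 ± 3 = Day 25 to 31, which lies inside Day 24 to 32. There is no conflict at Week 4.

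**5. Per protocol status of a Day 78 final sample.** Under SAP 2.1.2 with the protocol body (Day 77 to 91), it is in window and kept. Under SAP 2.1.2 with the synopsis (Day 80 to 88), it is out. Under SAP 3.4 with SAP 7.3, it is labelled Week 11 and excluded from a Week 12 result. SAP 3.4 is the more specific text, so the exclusion is what the plan prescribes if followed as written.

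**6. AUC.** The cut-off is 2 × (days) × (Week 0 value):

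- Day 77: 2 × 77 = 154 × Week 0 value.
- Day 84: 2 × 84 = 168 × Week 0 value.
- Day 91: 2 × 91 = 182 × Week 0 value.

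The estimated area changes with the end date too, so a move matters only for participants near the cut-off. A final sample on Day 77 to 79 with nothing after it ends the curve on its own date under the fallback, whatever its label. For a final sample on Day 89 to 91, SAP 7.2 does not say whether the curve ends there or at an earlier donation sample.

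**7. Donation samples.** Each donated unit carries a NAC sample, and donation is allowed up to twice weekly. The Week 12 range spans 88 − 80 + 1 = 9 days, so a donor still attending every 7 days has at least one sample inside it. Only donors who have stopped or lapsed can lack one, and the documents give no number for them.

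**8. After the fix.** If the final-visit sample is assigned to Week 12 anywhere in the reconciled window, 0 of 15 permitted days (±7) or 0 of 9 (±4) fall outside Week 12.

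**The case against.** The strongest reply is that little depends on this. The primary endpoint and the second secondary endpoint are both at Week 4. No endpoint is a Week 12 NAC value. The AUC uses the immunogenicity population, which has no Week 12 window rule, and counts actual days with a last-collection fallback. The SAP 7.3 ranges are introduced for summary tables, so on their face they do not govern the AUC. The per protocol set is used only if a sensitivity analysis is thought to be needed, and exclusion is by time point, so a participant keeps the other weeks. All of this stands and limits the point.

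A second reply is that a visit window and an analysis window do different jobs and may differ, as they do at Week 4. That is fair, and it makes SAP 1.6 against SAP 7.3 a mismatch rather than a plain contradiction. But at Week 4 the analysis window is the wider one, which is harmless. At Week 12 it is narrower, and SAP 3.4 then uses it to exclude values. The synopsis against the protocol body is a contradiction on any reading.

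A reader might infer from 6 of 15 days that 40% of donors lose their Week 12 value. The documents do not support that. It would need final visits spread evenly over the window and no donation sample on Day 80 to 88, and the donation schedule works against the second condition. A reader might also infer that ±7 is the intended window because it is stated more often. The synopsis and SAP 7.3 agree on ±4, and nothing in either document settles the matter.

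**Conclusion.** The plan is inconsistent as written and needs correcting, but the consequence is confined. A final-visit sample on Day 77 to 79 or 89 to 91 complies with the protocol body, yet SAP 3.4 and 7.3 label it Week 11 or 13 and exclude it from any per protocol Week 12 result, against SAP 2.1.2 read with the protocol body. This covers 6 of 15 permitted days. The share of participants cannot be derived from the documents. It depends on when final visits fall and how many donors have no Day 80 to 88 sample.

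Whether a Day 89 to 91 final sample ends the AUC is also undefined. That can alter the first secondary endpoint only for participants near the two-fold cut-off. The point does not reach the primary endpoint, and it does not mean that affected samples are lost from the AUC.

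The conclusion rests on two readings: that SAP 3.4 prevails over SAP 2.1.2 because it is more specific, and that the ±7 statements are operative. If ±4 is intended, SAP 7.3 already matches the visit window and the ±7 statements are what must change.

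**What to change.** 1. Reconcile the ±4 and ±7 statements to one visit window across the protocol synopsis, Protocol 5.2.2.6, note d to Table 1 in both documents, and SAP 1.6. The sponsor must say which is intended.
2. In SAP 3.4 and 7.3, assign the scheduled final-visit NAC sample to Week 12 whenever it falls inside that reconciled window. Leave the day ranges for other donation samples unchanged. Widening the range for every sample would make a 15-day Week 12 under ±7 and could give a twice-weekly donor several competing values.
3. State that, where a donor also has a donation sample labelled Week 12, the final-visit sample is the Week 12 value.
4. Apply the same rule to per protocol inclusion, so that SAP 2.1.2 and 3.4 agree.
5. In SAP 7.2, state that this sample is the Week 12 collection that ends the AUC. The existing last-collection fallback can remain for donors without collections through Week 12.

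The cost is protocol and SAP wording. No visit, blood draw or participant is added. The change should be made before NAC results are reviewed.
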